## Methodology:

This is a phase II clinical trial, with two cohorts of patients included in parallel, all with melanoma BRAF mutated and brain metastases without previous local treatment in the brain. Cohort 1 will include patients with asymptomatic brain metastases and cohort 2 will include patients with symptomatic brain metastasis.

BRAF mutation status will be tested locally using a validated test before patient inclusion, patients will receive both encorafenib 450 mg/day and binimetinib 45 mg/12 h (twice a day) (COMBO450) until progression disease (PD), toxicity or death. After 56 days of treatment, a contrast enhanced brain MRI and body CT scan will be performed as the first tumour assessment. Depending on the outcome of this image test, patients undergo local radiation treatment (radiosurgery or whole brain radiotherapy (WBRT) as per local radiotherapy oncologist. Encorafenib and binimetinib will be interrupted 24h before radiotherapy and restart 24h after the last dose of radiotherapy. After local treatment encorafenib and binimetinib will be administered at same doses until PD, toxicity or death. After progression, patients will be followed only for overall survival. In the case of COMBO450 is providing a clinical benefit to any patient, treatment could be continued, after agreement with Sponsor.

This study will be carried out following good clinical practices (GCP) guidelines as per European and Spanish regulations for clinical investigations.

Number of patients (planned): At least 63 patients.

Cohort 1: N=48; Cohort 2: N=15.

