- After progression, patients will be followed only for overall survival.
  - o In case of encorafenib and binimetinib are providing a clinical benefit to any patient, treatment could be continued after discussion with Sponsor if it agrees on that. In this case, follow up will be done as per institutional criteria. In the study, these patients will be followed only for overall survival.
- Study assessments: in each monthly visit, adverse events will be registered, blood samples will be collected for blood cell counts and general biochemistry (including magnesium, potassium and creatinine-kinases); an ECG will be performed at baseline, after one month of treatment, and every 3 months thereafter; a left ventricular ejection fraction (LVEF) evaluation will be performed by as per institutional guidelines at baseline and every 3 months thereafter ophthalmologic anamnesis and evaluation will be performed by oncologist at baseline and in every monthly visit, if there's any alarm symptom or sign, patient will be evaluated by Ophthalmologist. Body CT-scan and contrast enhanced brain MRI will be performed baseline and every 8 weeks up to 12 months and according to normal practise thereafter. More information regarding study determination is provided in section 8 of this protocol.

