# 8. STUDY ASSESSMENTS

# 8.1. Schedule for tests and determinations

Table 11. Schedule for tests and determinations

Visit	Baseline (D-28 to D-1)	w4	w8 (D-56)	Every 4w	Every 8w	Every 12 w	End of treatment (28 +/-4d)	FU before DP	FU after DP for OS
Informed consent	Х								
Screening registration	Х								
Histology confirmation of disease	Х								
BRAF Status	×								
Anamnesis	Х								
Demographics	Х								
Physical examination / vital signs	х	Х	х	Х			Х		
ECOG PS	×	Х	х	Х			X	Х	
Basic neurologic examination and Modified Barthel Index	Х	Х	X	Х			X	×	
Ophthalmologic anamnesis an evaluation by Oncologist	Х	X	X	Х			X		
Ophthalmologist exploration	If clinical suspicion								
ECG	×	Х				Х	×		
LVEF (as per institutional guidelines)	X					Х			
Concomitant medications	×	Х	Х	Х			Х		
Inclusion/exclusion criteria	×								
QoL	×	X at weeks 8 and 24							
Analytical tests									
Clinical laboratory test	×	Х	Х	Х			X	Х	
Pregnancy test	Х			Х			×		
Disease evaluation									
Abdominopelvic CT Scan (1)	Х		Х		X (³)			X (every 8w) (³)	
Brain MRI (  )	х		Х		X (³)			X (every 8w) (³)	

Colour Digital Photography (including a metric ruler) of skin lesions (¹)	х		Х		X (³)			X (every 8w) (³)	
Safety evaluation									
Adverse events and Serious Adverse events		Every 4 weeks throughout all the study (From ICF signature up to EoT visit)							
Study Treatment									
COMBO450 follow-up and dispensing		Х		х					
Dose reduction		Throughout all the study, when applicable							
Dose delay		Throughout all the study, when applicable							
Long term FU									
OS Follow-up									Х
New anti-cancer therapy									Х

 $(^1)$  Out of the assessments indicated by protocol, patients can be assessed whenever the investigator considers it indicated.

 Contrast enhanced MRI.

 $(^3)$  Assessments will be done every two months up to 12 months, thereafter, patients will be assessed as per institutional criteria.

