#### **Disease evaluation**

#### Radiological Assessment of Tumour Lesions

Body CT-scan and contrast enhanced brain MRI will be performed baseline and every 8 weeks (+/-1 week) up to 12 months and according to normal practise thereafter.

In addition, CT/MRI scans must be obtained of anatomic regions not covered by the chest and abdomen scans, in subjects where there is clinical suspicion for deep soft tissue metastases (e.g., lesions in the thigh). Such additional CT/MRIs will be required at Screening only when deep soft tissue disease is and must be consistently repeated at all tumour assessment visits if a deep soft tissue lesion is identified during Screening. In cases without suspicion for deep soft tissue disease, no such CT/MRIs are required.

Similar methods of tumour assessment and similar techniques must be used to characterize each identified and reported lesion at Screening during the treatment evaluation phases. Imaging-based evaluation is preferred to clinical examination. Helical (spiral) CT scans of chest and abdomen are preferred. If not available, conventional (non-spiral CT) should be used. If not contraindicated, IV contrast should be used for all studies. If IV contrast is contraindicated, MRI should be used at the Screening exam and at all tumour assessment time points. Oral contrast should be used for all applicable imaging unless contraindicated.

A reference measurement ruler must be printed on every image for scale determination. Sections should be contiguous, similarly sized and consistent from visit-to-visit. Section thickness must be based on institutional standards (e.g., from 5 to 8 mm, 10 mm cuts are not recommended). Chest x-rays and ultrasound are not acceptable methods to measure disease. Response and progression of disease must be documented by CT or MRI like the methods used at Screening.

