# 5. - Every 12 weeks until disease progression

- ECG
- LVEF

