performed within 6 months after database closure expected at 24 months after last patient inclusion, however interim analysis might be performed when analysing other primary variables

Percentage of patients (%) free of extracraneal progression at 6 (week 24), 12 (week 28) and 24 months (week 96): percentage of patients free of progression by RECIST 1.1 at 6 months (week 24), 12 months (week 48) and 24-month (week 96) considering date of inclusion. The final statistical analysis of this endpoint is expected to be performed within 6 months after database closure expected at 24 months after last patient inclusion, however interim analysis might be performed when analysing other primary variables.

**Overall Survival in both cohorts (OS):** OS is calculated as the time from date of inclusion to date of death due to any cause. The final statistical analysis of this endpoint is expected to be performed within 6 months after database closure expected at 24 months after last patient inclusion, however interim analysis might be performed when analysing other primary variables.

Percentage of patients (%) alive at 6, 12 and 24 months in both cohorts: percentage of patients alive at 6 months, 12 month and 24-month considering date of inclusion. The final statistical analysis of this endpoint is expected to be performed within 6 months after database closure expected at 24 months after last patient inclusion, however interim analysis might be performed when analysing other primary variables.

**Toxicity of the combination until local treatment:** Number of patients with adverse events and serious adverse events, changes in laboratory values, vital signs, electrocardiograms (ECGs), LVEF (MUGA (Multigated Acquisition Scan) / echocardiogram) and assessment of physician, dermatological and ocular examinations graded according to the National Cancer Institute (NCI) Common Terminology Criteria for Adverse Events (CTCAE) v 4.03 until local treatment (local treatment D1). It will be studied using descriptive statistics techniques, such as frequency tables and contingency tables. The final statistical analysis of this endpoint is expected to be performed within 6 months after database closure expected at 24 months after last patient inclusion, however interim analysis might be performed when analysing other primary variables.

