**Toxicity of the combination after local treatment:** Number of patients with adverse events and serious adverse events, changes in laboratory values, vital signs, electrocardiograms (ECGs), LVEF (MUGA (Multigated Acquisition Scan) / echocardiogram) and assessment of physician, dermatological and ocular examinations graded according to the National Cancer Institute (NCI) Common Terminology Criteria for Adverse Events (CTCAE) v 4.03 after local treatment (after end of local treatment date). It will be studied using descriptive statistics techniques, such as frequency tables and contingency tables. The final statistical analysis of this endpoint is expected to be performed within 6 months after database closure expected at 24 months after last patient inclusion, however interim analysis might be performed when analysing other primary variables.

**Quality of life:** Change from baseline in the global health status score of the EORTC QLQ-C30. The final statistical analysis of this endpoint is expected to be performed within 6 months after database closure expected at 24 months after last patient inclusion, however interim analysis might be performed when analysing other primary variables.

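### LVEF change is a component of toxicity before and after local treatment, but no post-baseline LVEF is scheduled before local treatment in patients irradiated by week 12

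*Combined protocol and SAP*

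**What the plan says.** **Endpoints (protocol 10.2).** Both toxicity endpoints list the same components, including "vital signs, electrocardiograms (ECGs), LVEF (MUGA (Multigated Acquisition Scan) / echocardiogram) and assessment of physician". The first is graded by CTCAE "v 4.03 until local treatment (local treatment D1", so it closes when local treatment starts. The second is graded "v 4.03 after local treatment (after end of local treatment date", so it opens only once local treatment is over. Both are summarised descriptively.

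**LVEF schedule.** Section 5.3 states that "a left ventricular ejection fraction (LVEF) evaluation will be performed by as per institutional guidelines at baseline and every 3 months thereafter". In Table 11 (section 8.1) the row "LVEF (as per institutional guidelines" is marked only under the baseline and 12-week columns. Section 8.2 places LVEF, with ECG, in the list headed "Every 12 weeks until disease progression". The week-4, week-8 and end-of-treatment lists do not contain LVEF. ECG is scheduled at week 4 and at the end of treatment.

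**Timing of local treatment.** The synopsis says "After 56 days of treatment, a contrast enhanced brain MRI and body CT scan will be performed as the first tumour assessment". Section 8.1 gives the imaging interval as "every 8 weeks (+/-1 week) up to 12 months". Under section 5.3, patients with neither intracranial CR nor PD, and no systemic PD, then go to radiotherapy. Patients with intracranial CR and no systemic PD stay on drug, with local treatment optional. Patients with PD stop drug. No latest date for starting radiotherapy is set.

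**SAP.** Section 5 (Safety analysis) has no LVEF table and no split of toxicity by local treatment.

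**The concern.** The window for toxicity on drug alone closes, for many treatment paths, before the first scheduled on-treatment LVEF. This matters because the grade 2 LVEF row of Table 10 describes an asymptomatic decrease, which only a measurement can reveal. If such a decline begins on drug alone in weeks 1 to 8, the schedule would first show it at week 12. By then the patient may already have been irradiated. The decline would be counted after local treatment, or in neither window, and the tables for the earlier window could look clean only because nobody looked.

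**Working it through.** **Denominators.** The plan states no figure for LVEF availability, so there is none to reproduce. Its cohort 1 sample size is used below only as a denominator, and it does reproduce:

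- n = [(1.645·√(0.4·0.6) + 0.842·√(0.6·0.4)) / 0.2]² = 37.1, rounded up to 38.
- 38 / 0.80 = 47.5, rounded up to 48.

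**Day count.** The first on-treatment LVEF is at 12 × 7 = day 84. I take it exactly on that day, since no tolerance is given for it.

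| Scan day | Days from scan to first LVEF |
|---|---|
| 49 | 35 |
| 56 | 28 |
| 63 | 21 |

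**Where the day-84 value falls.** Section 7.1.4.1 gives WBRT a length of 2 to 2.5 weeks, taken here as 14 to 17 days.

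| Start of local treatment | Window of the day-84 LVEF |
|---|---|
| Single-fraction radiosurgery by day 83 | After |
| WBRT of 14 days, start by day 70 (ends day 83) | After |
| WBRT of 17 days, start by day 67 (ends day 83) | After |
| WBRT start from day 71 (14 days) or day 68 (17 days) to day 84 | Neither: started but not finished |
| Any technique, start after day 84 | Before |

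A patient with PD at day 56 stops drug 28 days before the first LVEF is due. The end-of-treatment visit does not supply one.

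**Can the share affected be calculated?** Suppose 38 of 48 patients reach the scan and CR patients are not irradiated before day 84. Then the number with a scheduled post-baseline value before local treatment is

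CR + f × (38 − CR − PD),

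where f is the fraction of non-CR/non-PD patients irradiated after day 84. CR, PD and f are all assumptions; none is in the documents.

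| CR | PD | f | With a value | Of 48 | Of 38 |
|---|---|---|---|---|---|
| 10% | 0 | 0 | 3.8 | 8% | 10% |
| 20% | 0 | 0 | 7.6 | 16% | 20% |
| 30% | 0 | 0 | 11.4 | 24% | 30% |
| 60% (every planned response a CR) | 0 | 0 | 22.8 | 48% | 60% |
| 20% | 10% | 50% | 20.9 | 44% | 55% |
| 30% | 10% | 75% | 28.5 | 59% | 75% |

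For example, row five is 7.6 + 0.5 × (38 − 7.6 − 3.8) = 20.9. If all radiotherapy starts by day 84, fewer than half of the 48 enrolled have a value even in the all-CR extreme. With later radiotherapy that no longer follows.

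**The case against.** The strongest reply is that this is one component of descriptive secondary endpoints in a single-arm phase II trial, and that its reach is unknown. Several stronger readings are tempting, and the documents do not support them.

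- *Most patients lack a value.* With CR at an assumed 5 to 20% and all radiotherapy by week 12, one would infer that 80 to 95% of scanned patients lack one. The CR rate is not in the documents. Section 5.3 lets radiotherapy start when medically indicated, and makes later patients wait on the safety of the first three irradiated. Irradiation by week 12 is plausible but not prescribed.
- *Every early decline is credited to the wrong window.* Not so. If WBRT is running at week 12 the value belongs to neither window. If radiotherapy starts after week 12 it is correctly placed.
- *A planned before/after comparison is biased.* No comparison or test is specified. Section 10.2 describes frequency and contingency tables, and the SAP has no LVEF output.
- *Some patients never have an on-treatment LVEF.* The schedule shows only that none is planned. Unscheduled measurements are possible, and a symptomatic decline would be reported as an adverse event in its proper window.

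These points limit the size of the problem. They leave the mismatch standing: section 10.2 names LVEF in a window for which the schedule provides no post-baseline measurement in patients irradiated by week 12. The SAP's silence does not repair it.

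**Conclusion.** The endpoint definitions and the LVEF schedule do not fit together. For patients irradiated by week 12, no scheduled post-baseline LVEF precedes local treatment, and the week-12 value falls after it or in neither window. Patients stopped for PD at day 56 have no scheduled on-treatment LVEF. Unirradiated CR patients and patients irradiated after week 12 do contribute scheduled values.

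The timing result follows from the text, with LVEF taken on day 84. The proportion of patients affected does not, and no percentage should be attached to it. The consequence is one of interpretation: no asymptomatic LVEF decline in the earlier window would be weak evidence of cardiac safety on drug alone. The primary endpoint and the sample size are untouched.

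**What to change.** Reconcile the two toxicity definitions in protocol 10.2 with the LVEF schedule in section 5.3, Table 11 and section 8.2. In the analysis, do not tabulate LVEF separately by the two windows. Instead add one table to SAP section 5 giving:

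- LVEF change from baseline over the whole treatment period;
- the timing of each LVEF relative to the start and the end of local treatment;
- the number of patients with no on-treatment LVEF.

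The cost is a wording change and one table, with no new data, since the endpoint definitions already need the start and end dates of local treatment. The downside is that no separate LVEF statement can be made for each period. Whether to alter the LVEF schedule is for the sponsor to decide.

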- \*Radiosurgery: for patients who do not meet criteria for radiosurgery (RS) or (SRS), exceptional cases are allowed after prior detailed consultation with the trial coordinators.
  - After the first evaluation of the patient's intracranial response, patients without progression who received a local treatment, could receive other local treatments at the discretion of the investigator, if this is considered beneficial for the patient.
  - Surgery can be done if, as per investigator criteria, is necessary for the patient's health.
  - Patients with an intracranial CR not treated with radiation, if during follow up an only intracranial PD occurs, local treatment will be carried out as per protocol criteria. These patients can continue encorafenib and binimetinib treatment after local treatment if clinical benefit is considered by investigator.
  - All patients progressing by RECIST 1.1 criteria in body CT scan and/or by modified RECIST 1.1. criteria in contrast enhanced brain MRI, after having received local radiation therapy will discontinue systemic treatment with COMBO 450.

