#### Criteria for evaluation:

Efficacy assessment will be performed according to modified RECIST 1.1 criteria by contrast enhanced MRI for evaluating intracranial disease and according to RECIST 1.1 criteria by CT scan (PET-CT is also allowed) for evaluating systemic disease, every 8 weeks (+/-1 week) up to 12 months. If no PD during the first year, patients will be followed as per institutional criteria. Image technique should be consistent throughout the study. If no PD is observed after one year of follow up, patients will be followed as per institutional criteria, maintaining the treatment when clinical benefit is observed.

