## 5.3. Patient Inclusion and Cohort Assignment

During the screening (28 days before day 1 cycle 1) it should be assessed whether the patient is symptomatic (cohort 2) or asymptomatic (cohort 1).

Definition of Asymptomatic (cohort 1):.Patients without active symptoms secondary to brain metastases at the moment of inclusion.

After confirming that a patient fulfils all eligibility criteria of the study (inclusion/exclusion criteria), site staff will initiate the eCRF registration procedure.

Once procedure is fulfilled the site staff will receive the "Inclusion confirmation communication", and protocol-specific treatment can be initiated.

This is an open label, single arm study including two cohorts of patients, in each cohort, patients will be treated with encorafenib 450 mg once daily and binimetinib 45 mg twice daily.

After 56 days of treatment, a contrast enhanced brain MRI and CT body scan will be performed as first tumour assessment:

- Patients with PD at first evaluation in brain MRI (modified RECIST 1.1 criteria) and /or body CT scan (RECIST 1.1 criteria) will discontinue study treatment and will continue in the study for OS follow-up.
- Patients with CR in brain (modified RECIST 1.1) and no PD in the body (RECIST 1.1), will continue study treatment and will be followed every two months with contrast enhanced brain MRI and body CT scan up to 12 months. If no PD after one year, patients will be followed as per institutional criteria, and continue with the treatment.
  - o If considered by the investigator, local treatment can be done for brain CR patients, but only after confirming no safety concerns (defined as substantial deterioration of vital signs (including ECOG PS), physical examination, ECG, Lab. Values that do not recommend RT) with the three first patients treated with radiation therapy in the running phase (for more information, please see section 9.1).
- Patients with no CR and no PD in brain MRI per modified RECIST 1.1 criteria, and no PD in body per RECIST 1.1 criteria, will be treated with local RT and/or radiosurgery, and then will continue Enco and Bini. The first 3 patients will be treated in a running

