#### 10.5. Definition of study populations

Data of study will be analysed in the following populations:

- 1. ITT: All patients that have been enrolled in the trial.
- 2. Evaluable population per protocol (PP): All patients fulfilling all eligibility criteria and having at least two valid tumour assessments (baseline and one evaluation MRI or CT-scan) without any protocol deviation that makes the patient invalid for the primary endpoint evaluation.
- 3. Safety population: All patients receiving at least one dose of treatment.

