#### 10.6. Statistical analysis

For each categorical variable, the results will be summarized by frequencies and percentages. For each continuous variable, the results will be summarized by descriptive statistics such as median, range, and interquartile range or by means, standard deviations and 95% confidence intervals (CIs). For proportions, point estimates and exact 95% confidence intervals will be calculated. For time to event endpoints, Kaplan-Meier estimates at selected time points and corresponding curves will be presented. Time to event is derived relative to the first study treatment administration. Laboratory values will be expressed as the absolute values and as grading (ordinal categorical variables) according to NCI CTCAE v 4.03.

Treatment-emergent AE (AEs starting after the administration of study treatment and up to study completion) will be summarized by system organ class and preferred term. Grading will be presented by type and grade in tables showing frequency and percentage of the within-patient worst grades. In addition, grade ≥3 AEs will be summarized separately. Full analysis details will be outlined in the statistical analysis plan (SAP).

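### Toxicity until local treatment is counted to local treatment day 1 only, so complete responders who are irradiated late or never bring far longer exposure into the same percentage

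*Combined protocol and SAP*

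**What the plan says.** Toxicity of the combination until local treatment is a named secondary objective (Synopsis; protocol 4.2). Section 10.2 defines it as the number of patients with adverse events, graded by CTCAE "v 4.03 until local treatment (local treatment D1"). No alternative end is given for a patient who has no local treatment. On the summary, 10.2 says: "It will be studied using descriptive statistics techniques, such as frequency tables and contingency tables". Section 10.6 adds "tables showing frequency and percentage of the within-patient worst grades". The denominator is in 10.5: "Safety population: All patients receiving at least one dose of treatment".

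The treatment pathway fixes when day 1 of local treatment falls. The Synopsis (Methodology) says: "After 56 days of treatment, a contrast enhanced brain MRI and body CT scan will be performed as the first tumour assessment". Assessments are "every 8 weeks (+/-1 week) up to 12 months" (Synopsis, Criteria for evaluation). Patients with neither CR nor progression are then sent to radiotherapy. Patients in intracranial CR without systemic progression "will continue study treatment and will be followed every two months with contrast enhanced brain MRI and body CT scan up to 12 months" (5.3), and they stay on treatment after the first year if they have not progressed. Local treatment is optional for them. If they were not irradiated and later progress only in the brain, it is given at that time: "Patients with an intracranial CR not treated with radiation, if during follow up an only intracranial PD occurs, local treatment will be carried out" (Synopsis, Duration of treatment).

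SAP section 5 tabulates adverse events in the safety population. It has no split before and after local treatment, no cut-off date and no person-time rate. The SAP radiotherapy tables (4.3) do have rows for patients without radiotherapy, including those in CR.

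**The concern.** A count of patients with at least one event depends on how long each patient is watched. Here the length of the window depends on the patient's own response: it is short for patients with stable disease or partial response, who proceed to local treatment, and potentially very long for complete responders, who need not.

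Three readings of the result would suffer. The percentage would no longer describe a defined phase of treatment. It could not be set against toxicity after local treatment. Two groups with different CR rates, such as the symptomatic and asymptomatic cohorts, would show different percentages even with identical drug toxicity per month.

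**Working it through.** The documents state no figure for this endpoint, so there is nothing to reproduce. The check has two parts: window lengths from the documents, then an illustration of the effect on a percentage.

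**Window lengths**

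- *Neither CR nor progression at the first scan.* Week 8 ± 1 week gives 7 to 9 weeks. Nine weeks is 63 days, or 63/30.44 = 2.07 months. The interval from scan to local treatment day 1 is not stated and adds to this.
- *Intracranial CR, irradiated at later brain progression.* The window ends at that day 1. At month 10, for example, it is 10/2.07 = 4.8 times as long.
- *Intracranial CR, never irradiated.* The endpoint gives no end. By default the window ends when adverse-event collection ends. Protocol 8.1 and 9.4.1 put this at the end-of-treatment visit or resolution. The Synopsis (Safety), section 9 and section 10.6 refer instead to the end or completion of the study. Treatment runs until progression, toxicity or death, with no maximum.
- *Longest possible on the timetable.* Recruitment is 36 months (8.3) and the database closes 24 months after the last inclusion (10.2): 36 + 24 = 60 months for the earliest patient, or 60/2.07 = 29 times the 63-day window. At 24 months the ratio is 24/2.07 = 11.6. SAP 3.5 records 4 patients still on treatment at database closure.
- *Progression, death or dropout by the first scan.* Short windows, whether or not the patient is irradiated.

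**Illustration (hazards, shares and durations are assumptions, not document figures)**

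Assume a constant hazard h per month for a first grade ≥3 event, so risk(t) = 1 − exp(−h·t). A share s of patients stays unirradiated on drug for T months and the rest contribute 63 days:

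reported percentage = (1 − s)·risk(2.07) + s·risk(T)

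| h per month | 63-day risk | risk at 12 / 24 months | s = 10%, T = 12 / 24 | s = 15%, T = 12 / 24 |
|---|---|---|---|---|
| 5% | 9.8% | 45.1% / 69.9% | 13.4% / 15.8% | 15.1% / 18.8% |
| 3% | 6.0% | 30.2% / 51.3% | 8.4% / 10.6% | 9.7% / 12.8% |

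Worked entry: 0.90 × 0.098 + 0.10 × 0.451 = 0.088 + 0.045 = 13.4% (unrounded inputs).

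Dependence on the CR rate: at h = 5%, raising s by 5 percentage points adds 0.05 × (0.451 − 0.098) = 1.8 points at T = 12, or 0.05 × (0.699 − 0.098) = 3.0 points at T = 24, with the hazard unchanged.

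Patient-time: with s = 10%, the long-exposed patients supply (0.10 × 12)/(0.10 × 12 + 0.90 × 2.07) = 1.20/3.06 = 39% of all time in the window at T = 12, and 2.40/4.26 = 56% at T = 24.

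**The case against.** The endpoint is tied by its own wording to local treatment, not to day 56. A complete responder still on both drugs and never irradiated is experiencing toxicity of the combination without local treatment, and counting those events as such is a legitimate reading. This stands: the documents do not say that the window was meant to end at the first assessment, and a reader should not infer that. It does not rescue the summary, because unirradiated exposure of very unequal length still needs patient-time beside it, and none is planned.

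The endpoint is secondary and descriptive, the trial is uncontrolled, cohort 2 (N = 15) is exploratory, and no test or decision rule uses the result. This also stands and limits the harm. In the first row of the table, the shift from 9.8% to 13.4–15.8% is about 2 to 4 patients among 63. That lies inside the exact 95% interval for 6/63 (3.6% to 19.6%). The shift is nevertheless a bias in one direction that grows with response, and the interval does not describe it.

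The illustration gives every other patient a full 63 days, whereas protocol 10.1 assumes that 20% are lost, die or progress before day 56 without the first assessment. Investigators may also irradiate complete responders at any time, and toxicity that clusters early would shrink the effect. All true; these are reasons to treat the figures as illustrative.

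A tempting remedy is to cut every patient's window at day 63. That would lose data: a patient scanned on day 63 and irradiated on day 75 would have the events in between counted nowhere.

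**Conclusion.** The concern holds in a limited form. Applied as written, the endpoint pools roughly 8 to 9 weeks of exposure (plus scheduling delay) with many months or more in one unadjusted patient percentage, and neither the protocol nor the SAP corrects for it. The direction is clear: the percentage rises with the share of complete responders who are irradiated late or not at all. The size depends on that share, on their time on drug and on the event hazard, none of which the documents give.

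Three stronger readings are not supported. A reader might infer that the window never closes for unirradiated patients. It does close, when adverse-event collection ends, but at a different time for each patient, and the sections disagree on when collection ends. A reader might take 24 months as the longest window. It is not a documented cap, since the timetable allows up to about 60 months. A reader might assume that every unirradiated patient is long-exposed. Those who progress, die or leave early are not; the problem lies with the complete responders.

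The change is worth making because a named secondary safety endpoint becomes interpretable at little cost. The primary endpoint is unaffected.

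**What to change.** In protocol 10.2, and as an added table in SAP section 5:

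1. For patients irradiated following the first assessment, keep local treatment day 1 as the end of the window.
2. For patients not irradiated following the first assessment, close the window at the earlier of a fixed day tied to that assessment (for example day 63, the end of the week 8 ± 1 week window) and the end of their adverse-event collection.
3. Report the later events of this second group in a separate column for patients continuing without local treatment. It runs to local treatment day 1 if they are irradiated later, and otherwise to the end of adverse-event collection.
4. Show patient-time for every column.

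With these rules no on-drug event before local treatment day 1 is lost. State which end of adverse-event collection applies, since the sections differ.

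The cost is a few extra table columns and one derived date. The SAP listings already include event start dates, and the endpoint already needs the date of local treatment day 1, so no new data are required.

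While the section is open: the window after local treatment starts at the end of that treatment, so events from day 1 to its end (2 to 2.5 weeks for whole-brain radiotherapy, protocol 7.1.4.1) fall in neither window. This is a separate gap that the same table could close.
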